6.1.2. Week 12 EASI-75 Response

6.1.2.1. Main Analysis

- Estimand strategy: Composite, Estimand 1 (Section 2.1.1).
- Analysis set: FAS (Section 4).
- Analysis methodology: CMH and normal approximation in Section 5.2.1.
- Intercurrent events and missing data: The intercurrent event is captured through the variable definition; for participants who drop out for any reason, the response will be defined as “non-responsive” after that point.
- The number of participants, number and percent of response at Week 12 along with the 95% confidence interval by normal approximation will be presented for each treatment arm.
- The CMH test p-value, the estimate of the difference in proportions of response at Week 12 along with the corresponding 95% confidence interval by CMH normal approximation will be presented for each PF-04965842 dose group versus placebo.

6.1.2.2. Sensitivity/Supplementary Analyses

6.1.2.2.1. Supplementary Analysis - PPAS

An analysis that assesses the primary endpoint on the analysis set PPAS (Section 4). It will use the same methodology and summary as the main analysis.

6.1.2.2.2. Supplementary Analysis – Treatment Policy Estimand

- Estimand strategy: Treatment Policy, Estimand 3 (Section 2.1.3).
- Analysis set: FAS (Section 4).
- Analysis methodology: EASI-75 Response will be analyzed using a tipping point analysis in Section 5.3.1 including data from Weeks 2, 4, 8 and 12.
- Intercurrent events and missing data: All data collected will be utilized; missing values will be handled through multiple imputations as described by Tipping Point Analysis (Section 5.3.1 and Appendix 3).
- The number of participants, the number and percent of participants with missing response, and the estimate of response percentage at Week 12 along with the corresponding 95% confidence interval will be presented for each treatment arm.

- The estimate of the difference in proportions of response at Week 12 along with the corresponding p value and 95% confidence interval will be presented will be presented for each PF-04965842 dose group versus placebo.

6.2. Secondary Endpoint(s)

6.2.1. Key Secondary Endpoint - Weeks 2, 4, and 12 Peak Pruritus NRS4 Response

- Estimand strategy: Composite, Estimand 1 (Section 2.1.1).
- Analysis set: FAS (Section 4).
- Analysis methodology: CMH and normal approximation in Section 5.2.1. Participants must have baseline PP-NRS ≥ 4 to be included in the analysis.
- Intercurrent events and missing data: The intercurrent event is captured through the variable definition; for participants who drop out for any reason, the response will be defined as “non-responsive” after that point.
- The number of participants, number and percent of response at each specified timepoints along with the 95% confidence interval by normal approximation will be presented for each treatment arm.
- The CMH test p-value, the estimate of the difference in proportions of response at each specified timepoints along with the corresponding 95% confidence interval by CMH normal approximation will be presented for each PF-04965842 dose group versus placebo.

6.2.2. Key Secondary Endpoint - Change from Baseline in PSAAD at Week 12

- Estimand strategy: Hypothetical, Estimand 2 (Section 2.1.2).
- Analysis set: FAS (Section 4). Participants must have observed baseline measure to be included in the analysis.
- Analysis methodology: MMRM in Section 5.2.3 including change from baseline data for each Week from Weeks 1 – 12.
- Intercurrent events and missing data: All data collected will be utilized; a simple average of the available values recorded within a week will be used for the analysis as a weekly measure; if there’s no available values recorded within a week, PSAAD for the week is missing and will not be used for analysis.
- Number of participants included in the analysis will be presented for each treatment arm.
- The least square mean (LSM) of change from baseline in PSAAD along with the corresponding 95% confidence interval will be presented for each treatment arm at each Week.

- The LSM difference along with the corresponding p-value and 95% confidence interval will be presented for each PF-04965842 dose group versus placebo arm at each Week.

6.2.3. Secondary Efficacy Endpoints

6.2.3.1. Binary Endpoints

- Endpoints:
 - PP-NRS4 Response each day from Days 2-15 and Week 8;
 - Weeks 2, 4 and 8 EASI-75, IGA Response;
 - Weeks 2, 4, 8 and 12 EASI-50, EASI-90, EASI-100 Response;
 - Weeks 2, 4, 8 and 12 SCORAD50, SCORAD75;
 - Weeks 2, 4, 8 and 12 BSA <5% Response.
- Estimand strategy: Composite, Estimand 1(Section 2.1.1).
- Analysis set: FAS (Section 4). Participants must have baseline PP-NRS ≥ 4 to be included in the analysis of PP-NRS4.
- Analysis methodology: CMH and normal approximation in Section 5.2.1.
- Intercurrent events and missing data: The intercurrent event is captured through the variable definition; for participants who drop out for any reason, the response will be defined as “non-responsive” after that point.
- The number of participants, number and percent of response at each specified timepoints along with the 95% confidence interval by normal approximation will be presented for each treatment arm.
- The CMH test p-value, the estimate of the difference in proportions of response at each specified timepoints along with the corresponding 95% confidence interval by CMH normal approximation will be presented for each PF-04965842 dose group versus placebo.

6.2.3.2. Time to Achieve at Least 4 Points Improvement in the Peak Pruritus NRS from Baseline

- Analysis set: FAS (Section 4). Participants must have baseline PP-NRS ≥ 4 to be included in the analysis.
- Analysis methodology: Analyses for Time to Event Data in Section 5.2.5.

- Intercurrent events and missing data: For all participants who have not experienced the event, their time to event will be right censored at the last available measurement time.
- The number of participants, number and percent of participants censored and participants with Peak Pruritus NRS4 Response will be provided for each treatment arm.
- Estimated survival curves using the Kaplan-Meier method and number of patients at risk will be displayed graphically for each treatment arm. The 25%, 50% and 75% quartiles with their 95% confidence intervals will also be presented for each treatment arm.
- The log-rank test (stratified using baseline disease severity) p-value will be presented for each PF-04965842 dose group versus placebo.

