3.2.2. Secondary Efficacy Endpoints

- Response based on at least 4 points improvement in the Peak Pruritus NRS from baseline at all scheduled time points other than Weeks 2, 4 and 12.
- Time to achieve at least 4 points improvement in the Peak Pruritus NRS from baseline.
- Response based on the EASI-75 at all scheduled time points except Week 12.
- Response based on the IGA of clear (0) or almost clear (1) and 2 point reduction from baseline at all scheduled time points except Week 12.
- Response based on a $\geq 50\%$, $\geq 90\%$ and 100% improvement in the EASI total score (EASI-50, EASI-90 and EASI-100) at all scheduled time points.
- Change from baseline and Percent Change from Baseline in the percentage Body Surface Area (BSA) affected at all scheduled time points.
- Response based on BSA $< 5\%$ at Week 12.
- Percent Change from Baseline in EASI at all scheduled time points.
- Response based on a $\geq 50\%$ and $\geq 75\%$ improvement in Scoring Atopic Dermatitis (SCORAD50, SCORAD75) from baseline at all scheduled time points.
- Change from baseline and Percent Change from Baseline at all scheduled time points in Scoring Atopic Dermatitis (SCORAD) total score and subjective assessments sleep loss.
- Percent Change from Baseline in Peak Pruritus numerical rating scale (PP-NRS) from Days 2-15, Weeks 4, 8 and 12.
- Week 12 Corticosteroid-free days.
- Detailed descriptions of how the BSA and SCORAD are derived are provided in Appendix 5 and Appendix 8 respectively.

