5. GENERAL METHODOLOGY AND CONVENTIONS

5.1. Hypotheses and Decision Rules

PF-04965842 200 mg QD will be declared superior to placebo if the null hypothesis of no difference between PF-04965842 200 mg QD versus placebo for **both** co-primary endpoints is rejected at the 5% significance level. Similarly, PF-04965842 100 mg QD will be declared superior to placebo if the null hypothesis of no difference between PF-04965842 100 mg QD versus placebo for **both** co-primary endpoints is rejected at the significance level specified below.

[figure not shown]
The familywise Type-I error rate for assessing the co-primary and key secondary endpoints will be strongly controlled at 5% (2-sided) using a sequential, Bonferroni-based iterative multiple testing procedure.

The procedure will first assess the co-primary endpoints (IGA and EASI-75 at Week 12 for 200 mg QD vs placebo) at the 5% level. If this hypothesis is not rejected, then all subsequent hypotheses will not be considered statistically significant. If this hypothesis is rejected, then assessing for statistical significance will continue as follows:

- The hypothesis for severity of pruritus (Peak Pruritus NRS4) 200 mg QD vs placebo at Week 2 will be assessed at the 2.5% level. If this hypothesis is rejected, then the unused alpha level of 2.5% will be passed on to the assessment for the key secondary endpoints and the co-primary endpoints for 100 mg QD vs placebo, in the order specified in Sequence A at a 5% significance level (see figure below). All subsequent hypotheses from any point where a hypothesis cannot be rejected will not be considered statistically significant.

- If the hypothesis for severity of pruritus (Peak Pruritus NRS4) 200 mg QD vs placebo at Week 2) is not rejected at the 2.5% level, then the hypotheses for the key secondary endpoints and the co-primary endpoints for 100 mg QD vs placebo, in the order specified in Sequence A will be assessed at a 2.5% significance level (see figure below). If all hypotheses in this sequence are rejected, then the unused alpha level of 2.5% will be passed on to the assessment of the hypothesis for severity of pruritus (200 mg QD vs placebo) at Week 2 at the 5% level. All subsequent hypotheses from any point where a hypothesis cannot be rejected will not be considered statistically significant.

Figure 2. Schematic for Multiple Testing Procedure

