The figure above (Figure 2) illustrates the procedure showing the sequence of the tests. Hypotheses for all other endpoints not described here are to be tested at the nominal 5% (2-sided) significant level, without adjusting for multiple comparisons.

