Appendix 2. Definition and Use of Visit Windows in Reporting

Visit windows will be used for efficacy variables, and for any safety data that display or summarize by study visit. For other endpoints (eg, ECG, vital signs), visit windows will be applied for summary statistics by study visits if required.

Visit Label	Target Day	Definition [Day window]
Baseline	Day 1 (Day of first dose)	Last observation prior to and including day of first dose
Week 2	15	Days 2 to 22
Week 4	29	Days 23 to 43
Week 8	57	Days 44 to 71
Week 12	85	Days 72 to 99
Follow Up/End of Study		
Week 16	113	Days 100 to -

For the lab values, if the calculated study day for the labelled baseline visit is not study Day 1 but falls within 28 days before the start of the study dosing, then that data should be used for the baseline instead of leaving baseline missing.

For the other values, if the calculated study day for the labelled baseline visit is not study Day 1, but falls before the start of the study dosing, then that data should be used for the baseline instead of leaving baseline missing.

If two or more visits fall into the same window, keep the one closest to the Target Day. If two visits are equaled distant from the Target Day in absolute value, the later visit should be used.

Observations on the actual day will be used to analyze Days 2-15 Pruritus NRS. Weeks 2, 4, 8 and 12 Pruritus NRS will be based on the windowing method.

Safety analysis will follow CaPS.

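### The SAP tests Peak Pruritus NRS4 at Day 15 as an ungated nominal 5% endpoint, although Day 15 is the Week 2 target day and Week 2 is a gated key secondary endpoint

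*SAP*

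**What the plan says.** - **Key secondary.** Peak Pruritus NRS4 response at Weeks 2, 4 and 12 is a key secondary endpoint (SAP 3.2.1). SAP 5.1 tests the co-primaries for 200 mg first, at 5%, with a full stop on failure: "If this hypothesis is not rejected, then all subsequent hypotheses will not be considered statistically significant". After that, "The hypothesis for severity of pruritus (Peak Pruritus NRS4) 200 mg QD vs placebo at Week 2 will be assessed at the 2.5% level". If Week 2 misses that level but all of Sequence A is rejected at 2.5%, the unused alpha is "passed on to the assessment of the hypothesis for severity of pruritus (200 mg QD vs placebo) at Week 2 at the 5% level".
- **Non-key secondary, as defined.** SAP 3.2.2 lists NRS4 response "from baseline at all scheduled time points other than Weeks 2, 4 and 12". Protocol section 3 has the same exclusion.
- **Non-key secondary, as analysed.** SAP 6.2.3.1 lists "PP-NRS4 Response each day from Days 2-15 and Week 8", with a CMH p-value for each dose against placebo. SAP Appendix 1 lists the same days.
- **Level for everything else.** SAP 5.1 closes with "Hypotheses for all other endpoints not described here are to be tested at the nominal 5% (2-sided) significant level, without adjusting for multiple comparisons".
- **Data rules.** The Schedule of Activities puts Week 2 at Day 15. SAP Appendix 2 gives Week 2 the target Day 15 and a window of Days 2 to 22, and keeps the value nearest the target. For the daily series, "Observations on the actual day will be used to analyze Days 2-15 Pruritus NRS".

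**The concern.** The analysis section brings back, under a day label, the time point that the endpoint definition takes out. SAP 6.2.3.1 respects the exclusion for Weeks 4 and 12, since Week 8 is the only later visit it lists, but running the daily series to Day 15 readmits Week 2. Elsewhere the SAP treats the two as one time point: percent change in Peak Pruritus NRS is analysed on Days 2-15 and at Weeks 4, 8 and 12, with no separate Week 2.

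As a result, two decision rules apply to nearly the same comparison. Week 2 is the first key secondary test to receive alpha after the 200 mg co-primaries, and protocol 2.2.2 presents rapid itch relief as a differentiating feature and reports the Phase 2b NRS4 result by the Day 15 label. A Week 2 result that SAP 5.1 calls not significant could appear in the same report as a nominally significant Day 15 result.

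**Working it through.** **1. The plan's own figures.** Inputs (SAP 2.2): 75 per arm, two-sided 5%, IGA 12% vs 32%, EASI-75 23% vs 53%. Normal approximation: power = Φ{[d − z·√(2p̄(1−p̄)/n)] / √[(p₁q₁ + p₂q₂)/n]}.

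- IGA: p̄ = 0.22, so [0.20 − 1.96 × 0.0676] / 0.0656 = 1.03 and power is 84.8% (Fisher exact 80.7%).
- EASI-75: 97.2% (Fisher exact 96.1%).

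Both meet the stated minimums of 80% and 96%. The split in SAP 5.1 adds up: 2.5% + 2.5% = 5%. The documents state no power for NRS4.

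**2. The two tests side by side.**

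| | Week 2 NRS4 | Day 15 NRS4 |
|---|---|---|
| SAP section | 6.2.1 | 6.2.3.1 |
| Responder rule | at least 4 points | same |
| Participants | FAS, baseline at least 4 | same |
| Dropouts | non-response | same |
| Test | CMH by baseline severity | same |
| Value used | nearest Day 15 within Days 2-22 | Day 15 itself |
| Level, 200 mg | 2.5%, or 5% after recycling | nominal 5% |
| Gate | 200 mg co-primaries | none |

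Only the value rule differs in the data. It matters only for a participant still in the study with no Day 15 entry, who can have a Week 2 value but stays missing on Day 15 (SAP 5.3.1).

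**3. A borderline result.** 75 per arm, unstratified pooled z test, placebo 12/75.

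- Active 23/75: d = 0.1467, p̄ = 35/150 = 0.2333, SE = √(0.2333 × 0.7667 × 2/75) = 0.0691, z = 2.12, p = 0.034. This fails at 2.5% and passes at 5%.
- Active 24/75: d = 0.16, p̄ = 0.24, SE = 0.0697, z = 2.29, p = 0.022. This passes both.

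**4. How often the borderline case arises for 200 mg on the first pass.** This is the gap between power at 5% and at 2.5%, with placebo at 15.7% (Phase 2b, protocol 2.2.2) and no Day 15 entries missing.

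| Active rate | Source | Power at 2.5% | Power at 5% | Gap |
|---|---|---|---|---|
| 15.7% | null, exact | 2.4% | 5.1% | 2.7 points |
| 33% | assumed | 59.2% | 69.8% | 10.6 points |
| 41.1% | Phase 2b 100 mg | 89.6% | 94.0% | 4.4 points |
| 69.8% | Phase 2b 200 mg | about 100% | about 100% | negligible |

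Simulating the two tests directly gives 10.3% at an active rate of 33% and 3.9% at 41.1%.

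**5. The closed-gate case.** If the 200 mg co-primaries fail, SAP 5.1 leaves zero chance of a significant Week 2 result for either dose. Day 15 keeps its nominal rate, about 5% per dose under no itch effect (ignoring any correlation with the co-primary result) and more under a real effect.

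**6. Missing Day 15 entries.** The documents give no rate, so I assumed 0, 5, 10, 20 and 30% missing, with the replacement day copying the Day 15 status with probability 0.8. The null test statistics then correlate 1.00, 0.97, 0.95, 0.89 and 0.83. The null chance that Week 2 passes 2.5% or Day 15 passes 5% is 5.1, 5.2, 5.3, 5.6 and 5.8%.

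**The case against.** **Strong control was never promised for Day 15.** SAP 5.1 limits it to the co-primary and key secondary endpoints and labels everything else nominal and unadjusted. This stands. A reader might infer that familywise control fails for the itch claim, but it does not: only the SAP 5.1 procedure decides Week 2 significance, and nothing in 6.2.3.1 changes that. A reader might also take the chance that at least one dose reaches nominal 5% at Day 15 and set it against the 5% familywise rate. That comparison would apply to any unadjusted endpoint tested at both doses, Day 14 included, so it does not measure this defect.

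**The two are not the same endpoint.** This stands in part. Appendix 2 gives them different value rules, so they coincide exactly only when no Day 15 entries are missing. They are near-duplicates.

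**If Day 15 is the Week 2 hypothesis, the nominal sentence does not reach it, because that sentence covers only endpoints not described in SAP 5.1.** The reading is possible, but the SAP does not state it. Section 6.2.3.1 lists Day 15 as a separate endpoint with its own p-value, and the natural reading puts it under the nominal rule.

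**The 2.5% level is only a first pass.** This stands. If all of Sequence A is rejected, Week 2 is retested at 5% and the borderline conflict for 200 mg disappears. The order of Sequence A is in a figure not shown, so the position and level of a 100 mg Week 2 test cannot be checked. Closure after failure of the 200 mg co-primaries does not depend on that figure.

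**Day 14 would remain as a nominal itch result.** True. The fix does not prevent nominal early-itch claims. It removes the second rule on the Week 2 contrast itself.

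**Conclusion.** The contradiction is real, and its consequence is limited to reporting. SAP 3.2.2 excludes Week 2 from the non-key NRS4 endpoint, while SAP 6.2.3.1 and Appendix 1 test it again as Day 15 under a looser rule. The calls can part in two situations: a 200 mg p-value between 0.025 and 0.05 before any recycling, or failure of the 200 mg co-primaries, which closes Week 2 for both doses.

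The borderline situation has probability of about 10% at an assumed active rate of 33%, about 4% at 41.1%, and practically none at the adult Phase 2b 200 mg rate. If that rate carries over to adolescents on background topical therapy, only the closed gate matters for 200 mg. These figures assume 75 evaluable per arm, an unstratified test, placebo response of 15.7% and no missing Day 15 entries. The point is worth fixing before unblinding, but it does not undermine the testing procedure or the trial's primary conclusions.

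**What to change.** In SAP 6.2.3.1 and Appendix 1, change Days 2-15 to Days 2-14 for the tested NRS4 responses, leaving Week 8 as it is. Add one sentence to SAP 5.1: the Day 15 NRS4 comparison is the Week 2 key secondary comparison, and its significance is decided only by the procedure in that section. Day 15 can stay on the daily plot with its estimate and 95% confidence interval, without a p-value.

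This takes two line edits and one added sentence, and loses one nominal p-value per dose. No data collection, sample size or power for the co-primary or key secondary tests changes.

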6.2.3.3. Continuous Endpoints

- Endpoints:
 - Weeks 2, 4, 8 and 12 Change from Baseline and Percent Change from Baseline in %BSA;
 - Weeks 2, 4, 8 and 12 Percent Change from Baseline in EASI;
 - Weeks 2, 4, 8 and 12 Change from Baseline and Percent Change from Baseline in Total SCORAD score, SCORAD subjective assessments of sleep loss (VAS);
 - Percent Change from Baseline in PP-NRS from Days 2-15, Weeks 4, 8 and 12.
- Estimand strategy: Hypothetical, Estimand 2 (Section 2.1.2).
- Analysis set: FAS (Section 4). Participants must have observed baseline measure to be included in the corresponding analysis.
- Analysis methodology: MMRM in Section 5.2.3.
- Intercurrent events and missing data: All data collected will be utilized.
- Number of participants included in the analysis will be presented for each treatment arm.
- The least square mean (LSM) of change from baseline or percentage change from baseline along with the corresponding 95% confidence interval will be presented for each treatment arm at each specified time points.

- The LSM difference along with the corresponding p-value and 95% confidence interval will be presented for each PF-04965842 dose group versus placebo arm at each specified time points.

6.2.3.4. Week 12 Corticosteroid-free Days

- Definition: Number of days when neither topical nor systemic corticosteroids was taken (from Day 1 up to Week 12/Day 88 during the study treatment exposure period).
- Analysis set: FAS (Section 4).
- Analysis methodology: ANCOVA in Section 5.2.2.
- Intercurrent events and missing data: All data collected will be utilized.
- Number of participants, least square mean (LSM) along with the corresponding 95% confidence interval will be presented for each treatment arm.
- The LSM difference along with the corresponding p-value and 95% confidence interval will be presented for each PF-04965842 dose group versus placebo arm.

6.2.4. Patient Reported Outcomes

6.2.4.1. Continuous Endpoints

- Endpoints:
 - Weeks 2, 4, 8 and 12 Change from Baseline in in CDLQI, Anxiety and Depression Scales of HADS, POEM, DFI, PtGA and EQ-5D-Y (VAS score and index value).
- Estimand strategy: Hypothetical, Estimand 2 (Section 2.1.2).
- Analysis set: FAS (Section 4). Participants must have observed baseline measure to be included in the corresponding analysis.
- Analysis methodology: MMRM in Section 5.2.3.
- Intercurrent events and missing data: All data collected will be utilized.
- Number of participants included in the analysis will be presented for each treatment arm.
- The least square mean (LSM) of change from baseline along with the corresponding 95% confidence interval will be presented for each treatment arm at each specified time points.

- The LSM difference along with the corresponding p-value and 95% confidence interval will be presented for each PF-04965842 dose group versus placebo arm at each specified time points.

6.2.4.2. Change from Baseline at Week 12 in Peds FACIT-F

- Analysis set: FAS (Section 4). Participants must have observed baseline measure to be included in the analysis.
- Analysis methodology: ANCOVA in Section 5.2.2.
- Intercurrent events and missing data: All data collected will be utilized.
- Number of participants, least square mean (LSM) along with the corresponding 95% confidence interval will be presented for each treatment arm.
- The LSM difference along with the corresponding p-value and 95% confidence interval will be presented for each PF-04965842 dose group versus placebo arm.

